2.1.2 Phase II expansion

After the first 6 patients have been assessed for DLTs upon completion of cycle 1 of treatment, and the appropriate Cisplatin dose and Pembrolizumab dosing determined

for phase II expansion, an additional 41 patients with locally advanced larynx squamous cell carcinoma will be enrolled in this phase I/II study. The entire cohort will be used to assess the safety and efficacy outcomes of interest. Safety stopping rules will be applied in the event of excessive toxicity leading to inability of patients to receive at least 2 doses of cisplatin and complete radiation therapy. If radiation treatment breaks are required, greater than a 10 day radiation treatment break in 6 or more patients will also initiate early stop for safety evaluation.

Patients will be evaluated 14 weeks after completion of radiation (14 ± 2 week after completion of radiation) with radiographic imaging to assess response to treatment. All imaging will be assessed using Response Evaluation Criteria in Solid Tumors (RECIST) 1.1 Adverse events will be monitored throughout the trial and graded in severity according to the guidelines outlined in the NCI Common Terminology Criteria for Adverse Events (CTCAE) version 4.0.

After the end of treatment, each patient will be followed for a minimum of 30 days for adverse event monitoring (serious adverse events will be collected for up to 90 days after the end of treatment). Subjects will have post-treatment follow-up for laryngectomy event and survival status for two years.

Participation in this trial will be dependent upon supplying tumor tissue from a formalin-fixed specimen. Newly obtained formalin-fixed specimens are strongly encouraged 14-20 days after first dose of Pembrolizumab prior to initiation of cisplatin and radiation unless clinically deemed unsafe by the treating physician. The specimen will be evaluated for expression status of PD-L1.

2.1.2.1 Safety assessments during the Phase II expansion

[figure not shown]
This investigator initiated study will be under the oversight of the University of Cincinnati Cancer Consortium IRB and Data and Safety Monitoring committee. The investigators are ultimately responsible for monitoring the safety of patients who have entered this study and for alerting the Consortium IRB to any event that seems unusual in accordance with IRB policy. The investigator is responsible for the appropriate medical care of patients during the study. The investigator remains responsible to follow, through an appropriate health care option, adverse events that are serious or that caused the patient to discontinue before completing the study. The patient should be followed until the event resolves or stabilizes. Frequency of follow-up is left to the discretion of the investigator.

Safety measurements that will be used in the study include physical examinations and clinical laboratory tests (hematology and blood chemistries). The adverse event will be graded for toxicity using the NCI CTC version 4.0. Toxicity assessment will occur at the start of each cycle, or more frequently if clinically indicated. Any adverse events leading to a treatment interruption or dose reduction along with all adverse events that are grade 3 and higher will be recorded in the CRF.

The criteria for dose de-escalation for adverse events are outlined in Section 5.2. Any patient who requires two dose modifications or de-escalations will be taken off study.

2.2 Trial Diagram

Please refer to timing of treatment administration (section 5.2.1.4) Trial Flow Chart (section 6.0) for details on timing flexibility of treatment administration.

3.0 OBJECTIVE(S) & HYPOTHESIS(ES)

3.1 Primary Objective(s) & Hypothesis(es)

3.1.1 Primary Objective & Hypothesis for phase 1 safety run-in portion:

Objective: Determine the safety and tolerability of **Pembrolizumab** in combination with **cisplatin and radiation** patients with **LA-larynx SCC**.

Hypothesis: The combination of Pembrolizumab with cisplatin and radiation is safe and well tolerated in patients with LA-larynx SCC.

3.1.2 Primary Objective & Hypothesis for phase 2 portion:

(1) **Objective:** Determine the 18-month laryngectomy-free survival in locally advanced laryngeal squamous cell carcinoma (LA-larynx SCC).

Hypothesis: Patients with LA-larynx SCC who receive Pembrolizumab combination with Cisplatin and radiation have a 15% improvement in 18-month laryngectomy-free survival.

3.2 Secondary Objective(s)

- (1) **Objective:** Estimate the one-year laryngectomy-free survival in locally advanced laryngeal squamous cell carcinoma (LA-larynx SCC).
- (2) **Objective:** Estimate overall survival and progression free survival in patients enrolled in the study
- (2) **Objective:** Estimate 3-month complete response rate (CR) in patients enrolled in the study
- (3) **Objective:** Estimate event –free survival (events include death, persistent or progressive disease, laryngectomy)

3.3 Exploratory Objective

1. **Objective:** Explore peripheral T cell phenotype at baseline and after treatment with Cisplatin, radiation, and Pembrolizumab.
Hypothesis: T cell phenotype is altered after exposure to Cisplatin, radiation, and Pembrolizumab, and will correlate with treatment response.
2. **Objective:** Measure expression of the proteins in the PD-1 family on baseline tumor samples and on treatment biopsies.
Hypothesis: There is a relationship between response to Pembrolizumab and PD-1 protein family expression in both pre- and post-treatment tumor samples. Cisplatin-radiation concurrent with Pembrolizumab impacts the expression of PD-1 family of proteins.
3. **Objective:** Measure circulating tumor DNA in pre-treatment, during treatment, and post-treatment blood samples.
Hypothesis: There is a relationship between response to Pembrolizumab and circulating tumor DNA level in both pre- and post-treatment tumor samples.
4. **Objective:** Explore Tumor infiltrating immune cell phenotypes and global gene expression (including 12-gene signature) by RNAseq on baseline tumor samples and on treatment biopsies.
Hypothesis: Tumor infiltrating immune cell phenotypes and global gene expression is altered after exposure to Pembrolizumab, and will correlate with treatment response.
5. **Objective:** Explore patterns of disease recurrence after treatment with Cisplatin, radiation, and Pembrolizumab.
Hypothesis: Patterns of recurrence of disease is altered after exposure to Pembrolizumab when added to standard Cisplatin and radiation therapy.
6. **Objective:** Explore rates of speech and swallowing dysfunction after completion of treatment with Cisplatin, Radiation, and Pembrolizumab.
Hypothesis: Rates of speech and swallowing dysfunction is improved after completion of treatment with Cisplatin, Radiation, and Pembrolizumab.
7. **Objective:** Explore PET scan findings after completion of treatment with Cisplatin, Radiation, and Pembrolizumab

Hypothesis: There is a relationship between post treatment PET scan and clinical benefit in patients treated with Cisplatin, Radiation, and Pembrolizumab.

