Laryngeal squamous cell carcinoma is unique in the setting for which surgical options are less appealing due to long-term morbidities associated with a total laryngectomy (tracheostomy and loss of voice). Chemo-radiation alone may not be sufficient to avoid surgery and allow for a long-term survival of patients with a functional larynx. This disease is also unique in the setting that it is highly associated with smoking and genetic complexity, making it a favorable target for immune modulators. In addition, biologic correlative testing is feasible due to the accessibility of tumor tissue by biopsy and any specimens from patients undergoing laryngectomy for residual/ progressive or dysfunctioning larynx.

We propose a single arm phase II study to test the hypothesis that the addition of Pembrolizumab to chemoradiation enhances the local effects of standard therapy in laryngeal HNSCC, ultimately allowing for higher rates of functional organ preservation in this population, and leading to improved quality of life. In addition, we hypothesize that adding Pembrolizumab to chemo radiation may result in immune-mediated regression

of micrometastatic disease and lower rates of systemic relapse, similar to what has previously been described in distant untreated melanoma lesions [21] Therefore, we will examine not only laryngectomy-free survival and event-free survival endpoints [including death, persistent disease or progression, laryngectomy (partial or total), and feeding tube dependence], but also pattern of in and out of field tumor growth in these patients. Finally, we will examine exploratory correlative studies that will provide valuable insight into the effects of chemo radiation in combination with PD1 inhibitor on laryngeal carcinoma microenvironment, and the association of tumor response and overall clinical benefit with adaptive PD-L1 tumor expression, immune infiltration, cytokine expression profiles, and genomic signature of tumors. We hypothesize that chemo radiation affects expression of PD1/PD-L1 on tumor infiltrating immune cells detected by IHC and subsequently increases PD-L1 expression on the tumor cells, which will predict response to chemo radiation and PD-1 inhibitor.

We hypothesize by inhibiting PD1 ligands, PDL1 and PDL2, we will activate immune system and allow for better anti-tumor effect, finally resulting in improved laryngectomy-free survival with fewer side effects.

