Treatment cycle/Title:	Main Study Screening Visit	C1 D-21	C1 D1	C1 D2 2	C1 D43	At time of Discon	30 days post discon	Every 12 weeks (± 1 w)	Every 12 weeks (±1 w)
Scheduling Window (Days):	-28 to -1	-21 to -14	± 2	± 2	± 2				
Correlative Studies Blood Collection	x		x					x£	
Urinalysis	x		x		x				

∅ Recommended but not mandatory

£ Only once 12-16 weeks after end of treatment

¥ At 3, 6, 12 months after end of treatment

△ Continuous daily

€ If patient and clinician need to expedite initiation of chemoradiation, they are allowed to start cisplatin and radiation after a minimum of 14 from first dose pembrolizumab, however, there should be a minimum of 21 days (+/- 2 days) between pembrolizumab doses, thereafter.

∞ patients should be contacted by telephone every 12 weeks to assess for survival status until death, withdrawal of consent, or the end of the study, whichever occurs first

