7.1.2.7 Tumor Tissue Collection and Correlative Studies Blood Sampling

All patients will be required to submit archival tissue as part of study participation. In patients who do not have archival tissue, a pretreatment tumor biopsy will be performed, unless deemed contraindicated by the treating physician. An attempt to obtain additional tumor biopsies will be performed after 1 dose of treatment if felt safe and feasible. These samples will be submitted centrally for immunohistochemical expression studies involving proteins in the PD-1 family as well as CD3, CD69 and FOXP3. We will also attempt to perform Tumor infiltrating immune cell phenotypes, global gene expression by RNAseq, and whole genome sequencing if adequate tissue available.

Research blood collections will be obtained for correlative research studies on the following time points: Prior to initiation of therapy (day -21 cycle 1), after 1 dose of treatment (day 1 cycle 1), at treatment discontinuation and 14 +/- 2 weeks follow up. We intend to perform flow cytometric evaluation of CD3, CD4, CD8, CD14, PD-1, PD-L1, PD-L2 on peripheral blood mononuclear cells as well as measurement of circulating tumor cells and circulating cell-free DNA.

Specimen Requirements: Submission for flow cytometry

- A 7.5 mL specimen of peripheral blood in a lavender- (EDTA) or green- (sodium heparin) tube is acceptable for each draw.
- Storage/Transport Temperature: Specimens can be transported with a cold pack or wet ice, but do not fix or freeze specimens.
- Unacceptable Conditions: Frozen specimens, specimens greater than 48 hours old, specimens fixed in formalin for flow cytometry
- Address for shipping specimens: Please refer to Standard Operating Procedures for details on blood and tissue shipment:

[name], Sr. Research Assistant

University of Cincinnati Retrovirology Reference Laboratory

[name]

Lab: [contact]

Office: [contact]

[contact]

Email: [contact]

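### The scheduled biopsies capture one dose of pembrolizumab and no chemoradiation, so they cannot test the tissue hypothesis in objective 2; separately, the flow chart omits the blood draw at treatment discontinuation that Section 7.1.2.7 lists

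*Combined protocol and SAP*

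**What the plan says.** **Hypotheses.** Objective 2 in Section 3.3 is to "Measure expression of the proteins in the PD-1 family on baseline tumor samples and on treatment biopsies". It carries two hypotheses: that response is related to PD-1 family expression in tumor samples from before and after treatment, and that "Cisplatin-radiation concurrent with Pembrolizumab impacts the expression of PD-1 family of proteins". Section 4.2.1 says "We hypothesize that chemo radiation affects expression of PD1/PD-L1 on tumor infiltrating immune cells detected by IHC". It adds that PD-L1 on tumor cells rises as a result and that this will predict response.

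**Tissue.** Section 2.1.2 says that new specimens are "strongly encouraged 14-20 days after first dose of Pembrolizumab prior to initiation of cisplatin and radiation". Section 7.1.2.7 says "An attempt to obtain additional tumor biopsies will be performed after 1 dose of treatment if felt safe and feasible". In the flow chart (Section 6.1) the tissue row is marked at screening and at C1 D1 and nowhere later. Section 4.2.3.2 also foresees tissue from salvage laryngectomy and possible biopsies of recurrence.

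**Blood.** Section 7.1.2.7 asks for a draw before therapy, then "after 1 dose of treatment (day 1 cycle 1), at treatment discontinuation and 14 +/- 2 weeks follow up". In the flow chart, the row "Correlative Studies Blood Collection" is marked at screening, at C1 D1, and once at 12 to 16 weeks after the end of treatment. The discontinuation cell is empty.

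**The concern.** An effect of chemoradiation on tumor can be seen only in tumor sampled after some chemoradiation has been given. If the one scheduled on-treatment biopsy comes before it, the comparison named in objective 2 answers a different question. A change seen in the pair would belong to pembrolizumab alone, while the hypothesis printed beside it speaks of the combination.

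The blood question is independent of this. Two parts of the protocol disagree on the number of draws, and a time point that a site skips cannot be collected later. The draw at stake is the only one between the start of chemoradiation and the 14-week visit. It serves the work on T-cell phenotype (objective 1) and circulating tumor DNA (objective 3).

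**Working it through.** The plan states no figure for this point, so the check sets the sections side by side and adds simple counts.

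**1. Exposure at the on-treatment biopsy.**
- Section 2.1.2 places the biopsy 14 to 20 days after the first pembrolizumab dose and before cisplatin and radiation.
- The flow chart marks it at C1 D1. Section 5.2.1.4 says that Day 1 procedures are completed before dosing, so a C1 D1 biopsy also precedes chemoradiation.
- Table 2 gives the full course as up to 4 pembrolizumab doses, up to 3 cisplatin doses and 35 fractions.
- Exposure at biopsy is therefore 1 pembrolizumab dose, 0 of 3 cisplatin doses and 0 of 35 fractions.
- The flow-chart mark points to the footnote for recommended, non-mandatory items, so not every patient will have the pair.

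**2. Tissue after chemoradiation.** No such sample is scheduled at D22, D43, discontinuation or follow-up. What remains is salvage laryngectomy and recurrence tissue. Section 8.1 allows a rough upper bound on laryngectomy specimens, because a first laryngectomy is an event for laryngectomy-free survival (LFS):

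expected events by 18 months = 47 × (1 − LFS)

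- LFS 85%: 47 × 0.15 = 7.05, about 7
- LFS 70%: 47 × 0.30 = 14.1, about 14

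These events include deaths, so laryngectomy specimens would be fewer. The bound does not cover biopsies of recurrence without laryngectomy. Patients who stay free of disease with a working larynx contribute no tissue after chemoradiation, so expression after treatment cannot be compared between them and the rest.

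**3. Blood time points.**

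| Time point | Section 7.1.2.7 | Flow chart |
|---|---|---|
| Before therapy | yes | yes (screening) |
| C1 D1, after one pembrolizumab dose | yes | yes |
| Treatment discontinuation | yes | **no mark** |
| 14 ± 2 weeks (12 to 16 weeks) | yes | yes |

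The vital-signs and ECOG rows do carry a mark in the discontinuation column, so the column is in use and the empty cell is unlikely to be a fault of text extraction.

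Gap without a sample under the flow chart = 7 weeks of radiation (Table 2) + 12 to 16 weeks = 19 to 23 weeks. With the discontinuation draw, this splits into about 7 weeks and 12 to 16 weeks.

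**4. Wording elsewhere.** Objective 4 uses the same baseline and on-treatment biopsies and claims only a change after pembrolizumab exposure, which fits the sampling. Objectives 2 and 3 speak of response to pembrolizumab, but the protocol's scheduled response imaging comes 14 ± 2 weeks after radiation ends, that is, after all three treatments (Sections 2.1.2 and 7.1.2.6). Items 1 to 3 of Section 4.2.3.2 already tie response or benefit to the combination.

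**The case against.** **On tissue.** A reader might infer that the chemoradiation hypothesis cannot be tested at all. The documents do not support that. Section 7.1.2.7 plans PD-1, PD-L1 and PD-L2 on blood mononuclear cells, including at 14 ± 2 weeks, and Section 4.2.3.2 plans PD-L1 on circulating tumor cells. Both can give measurements after chemoradiation. This part of the objection stands. It does not rescue the tissue claim, because objective 2 names tumor samples and Section 4.2.1 names tumor-infiltrating cells. Nor can a single arm separate chemoradiation from pembrolizumab in the later blood samples.

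A reader might also infer that tissue after chemoradiation comes from treatment failures only. Sections 4.2.1 and 4.2.3.1 foresee laryngectomy for a dysfunctional larynx as well. Such patients may have responded, although their specimens may hold no tumor, and a patient who recurs may have had a complete response at 14 weeks. The sample is selected, but not made up solely of non-responders.

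It is also fair to say that no analysis text assigns the paired-biopsy difference to chemoradiation, and that the biopsy timing is stated openly. Misattribution is a risk that the hypothesis invites, not something the plan prescribes. The claim about predicting response is in Section 4.2.1, not in objective 2.

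**On blood.** Section 7.1 calls the flow chart a summary, so a site reading Section 7.1.2.7 would take the draw. But Section 5.9 sends the reader to the chart for prescribed times and windows, and Section 7.1.5 does so for visit requirements. No rule of precedence is given. It is true that neither objective 1 nor objective 3 names an end-of-treatment sample. Objective 1 keeps a baseline and a post-treatment draw, and objective 3 keeps C1 D1 as a draw during treatment. The loss would weaken these objectives, not remove them.

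**Conclusion.** Both defects hold, and they are separate.

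- **Tissue.** The scheduled pair measures the effect of one pembrolizumab dose. It cannot test a chemoradiation effect in tumor. The remaining tissue is too few, unscheduled and selected to support a link between post-treatment expression and response.
- **Blood.** One of the four draws in Section 7.1.2.7 has no mark in the flow chart. The gap of 19 to 23 weeks applies only to a site that works from the chart alone, and assumes a 7-week radiation course without breaks.

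The bound of about 7 to 14 LFS events rests on the plan's 85% and 70% rates and on all 47 patients being followed to 18 months. The reach is limited to exploratory objectives: the primary and secondary endpoints, the sample size and the safety rules are untouched. The reference to response to pembrolizumab in objectives 2 and 3 is a minor wording point. The changes are worth making because they alter what the trial can validly conclude from its biopsies and protect a sample that cannot be recovered.

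**What to change.** 1. In objective 2 and Section 4.2.1, limit the tissue hypothesis to what the pair can show. For example: *one dose of pembrolizumab, before chemoradiation, changes PD-1 family expression in tumor, and the change is associated with outcome after combined treatment*.
2. State that salvage laryngectomy and recurrence tissue is analysed descriptively.
3. Keep any before-and-after question about the combination for the blood-cell and circulating-tumor-cell measures already planned, and note that a single arm cannot separate the components.
4. Mark the discontinuation cell in the flow-chart row for correlative blood, to match Section 7.1.2.7.
5. In objectives 2 and 3, refer to response to pembrolizumab plus chemoradiation, in line with Section 4.2.3.2.

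The cost is a few sentences and one flow-chart cell, with no new biopsy and no draw that Section 7.1.2.7 does not already list. The price is a narrower biological claim from tissue.

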4.0 BACKGROUND & RATIONALE

4.1 Background

4.1.1 Laryngeal cancer

Laryngeal cancer represents one of the more common head and neck malignancies, accounting approximately for 20% of all cases, majority of them (85-90%) being squamous cell carcinomas [1, 2]. Up to 40% of patients present with advanced disease [3]. The term advanced laryngeal cancer generally denotes stage 3 or 4 laryngeal cancers according to the Union for International Cancer Control (UICC) / American Joint Committee on Cancer (AJCC) staging. Since larynx is essential in many physiologic functions including speech production, swallowing, airway protection, and breathing, disruption of any of these functions by either the tumor or the treatment may have devastating consequences for the patient and often associated with significant morbidity and mortality for the patient and a financial costs for society [4, 5]. Therefore, in addition to achieving tumor control, optimizing functional outcomes and organ preservation are very important in treatment of patients with laryngeal carcinoma.

Management of advanced laryngeal cancer is complex and involves different treatment modalities [6]. Total laryngectomy (TL), alone or with neck dissection (ND), radiotherapy (RT) alone, TL followed by RT, and combined chemotherapy and RT (CRT) [6, 7] are considered standard treatment options. Prior to 1991, TL followed by adjuvant RT was widely considered the standard management option [8]. This approach would result in permanent tracheostoma in the neck, alterations in deglutition and loss of natural voice for the patients. The Veterans Administration (VA) study in 1991 sparked a major change in the management of advanced laryngeal cancer. [9] This randomized study involving 332 patients found that induction chemotherapy followed by radiation therapy achieved an equivalent 2 year survival rate (68%) compared with total laryngectomy with postoperative radiation therapy. Moreover, the larynx could be preserved in 64% of patients undergoing chemoradiation therapy. Overall 64% of patients receiving chemoradiation achieved histologically confirmed complete response [9]. No significant difference in survival was reported after more than 10 years of follow up [10]. Patterns of recurrence differed significantly between the two groups with more local recurrences (12% vs 2%) and fewer distant metastases (11% vs 17%) in the chemotherapy group than in the surgery group. Thus addition of chemotherapy to radiation introduced new oncologic end points, namely organ preservation and laryngectomy-free survival (LFS). [9]

The VA study was followed by another landmark study, the Radiation Therapy Oncology Group (RTOG) 91-11 trial reported by Forasteire and colleagues in 2003. This three arm randomized controlled trial in 547 locally advanced (stage III and IV – T2, T3 or low volume T4) resectable laryngeal cancer patients confirmed significantly lower rates of salvage laryngectomies in chemoradiation treated patients. [11] By the end of 2 years, the proportion of alive patients with intact larynx after radiotherapy with concurrent chemotherapy was 88% vs 75% in the group that received induction chemotherapy followed by radiotherapy vs 70% in the radiotherapy group alone, the differences being

statistically significant. Overall survival rates were similar at 75% at 2 years for all treatment groups [11]. In a recent update to the RTOG 91-11 study, composite end point of LFS for the concurrent chemotherapy group was 74% and 63% at 1 and 2 years respectively. At 10-year follow up, there is no significant difference between the concomitant cisplatin/ RT arm (23.5%) and the induction arm (28.9%). LFS was significantly worse for RT group (17.2%) versus both the induction group and the concomitant group, confirming role of systemic therapy in treatment of laryngeal cancer. [12]

More recent studies that have introduced more aggressive induction chemotherapy regimens [TPF (taxane, cisplatin, and 5-fluorouracil)] to improve on laryngeal preservation rates compared to induction chemotherapy arm of RTOG 91-11 (3-year LFS 70% vs 57%), however, these regimens carry higher adverse events without improvement in PFS or OS. [13]

In the event of locally recurrent, residual disease, or dysfunctional larynx after completion of chemo radiation, salvage laryngectomy is considered standard treatment. However, there appears to be a significantly worse survival outcome for those patients undergoing laryngectomy after patients having been exposed to chemotherapy in combination with radiation [12].

Thus, treatment paradigms for larynx cancer have continued to change since 1991 resulting in variability in the treatment sequence and type of therapeutic modalities used. [14]. Unlike most other malignancies, a recent review of the latest National Cancer Data Base (NCDB) has demonstrated worsening survival outcome of larynx cancer patients in recent years with a 5-year survival at 59% compared to 67% in 1985. These findings may, to some extent, reflect changes in practice patterns over the last two decades [1]. In addition, some other retrospective studies suggest a possible inferior oncologic outcome in patients who choose organ preservation compared to a more traditional upfront surgery (TL) with 2-year disease specific survival and overall survival (70% vs 64%) and (64% vs 57%) respectively. [15]

These findings suggest a need for further investigation and development of more successful curative organ preservation approaches. Despite multiple trials over the last two decades, overall rates of cure and organ preservation remain suboptimal without much improvement since introduction of concurrent chemo radiation in the landmark RTOG 91-11 study.

